1.0 GENERAL INFORMATION

50,098/ IND/Date of submission

CPP Protocol #/Date Approved No. / (mm/dd/yy) Department of Defense (DOD) Sponsor

Office of The Surgeon General of the Army

Commander Sponsor Representative:

U.S. Army Medical Materiel Development Activity

(USAMMDA) [name]

[name]

[contact]/[name]

[contact]

Institut Pasteur, Tunisia Principal Investigator:

[name] [name], PhD [contact] [contact]-

[name]

Subinvestigators: Institute Pasteur, Tunisia

[name] [contact] [contact]-

[name]

Scientific Expert and Consultant: Pôle de Recherche Biomédicale, Centre Médical de

[name], PhD l'Institut Pasteur, Institut Pasteur,

[name]

[contact] [contact]

Tripler Army Medical Center Study Coordinator and Consultant:

[name] Department of Clinical Investigation

Honolulu, Hawaii

[contact]

Coordinator and logistical support

Pôle de Recherche Biomédicale du Centre Médical [name]

de l'Institut Pasteur, Institut Pasteur,

[name] [contact] [contact]-

[name]

Monitor: **USAMMDA**

Ft. Detrick, MD

[contact]

[name], R.N.

Medical Monitor Institut Pasteur de Tunis

[name] [name] [name],

Tunisia

[contact]

Protocol: A-9768.2 Ver 9.0 14 March 2010 Phase 2 WR 279,396 Study in Tunisia

Office of The Surgeon General Department of the Army

Study Location: Tunis, Tunisia

Institut Pasteur de Tunis

Institute Pasteur, Tunis, Tunisia [name],

Tunisia

Study Duration: 17 Months

Anticipated Start Up Date: November 2005

Required No. of Volunteers: 40

TABLE OF CONTENTS

1.0	GENERAL INFORMATION	2
2.0	BACKGROUND	6
3.0	STUDY SUMMARY	6
4.0	STUDY OBJECTIVES	7
5.0	FACILITIES TO BE USED	8
6.0	BACKGROUND OF LEISHMANIASIS	8
	6.1 Natural history and drug treatment of Old World cutaneous leishmaniasis	8
	6.1.1 Old World cutaneous leishmaniasis	8
	6.2 Present topical agents	10
	6.3 WR 279,396 Preclinical Efficacy	11

2.0 BACKGROUND

An analysis of the data from the recent WR 279,396 study (HSRRB Log # A-9768.1) indicates that by day 50, cure rate was 91.8% in the treatment group and 73.2% in controls ($x^2 = 5.60$, p= 0.017) and complete cure response was 95.8% among the former versus 75% among the latter ($x^2 = 8.04$, p= 0.004). The global healing rate is already much higher than the previous (placebo) 25% healing rate in the same area using the same evaluation criteria (Ben [name] 95). The occlusive dressing used during the ongoing trial may have positively influenced the healing rate, by enhancing drug diffusion into the deep dermis and accelerating the reepithelialization process. The practicability of polyurethane adhesive dressings was not perfect however. Local reactions (mild pain, redness and edema) was noticed among 22 patients (11 among the treatment group (22.4%) and 11 among controls (28.6%), NS. Although no patient stopped drug applications, topical treatment might be improved by simplifying the regimen. WR 279,396 without occlusion was superior to placebo in a Colombian Phase 2 study (Soto 02) making it the reference schedule. No tolerance problems were observed in this trial.

The Office of the Surgeon General, United Sates Army represented by USAMMDA holds the IND for WR 279,396 and will continue the development of the product through a commercial pharmaceutical partner in order to obtain licensure by the FDA.

Thus, this Phase 2 study is to determine whether WR 279,396 with occlusion (a polyurethane dressing) is more effective than WR 279,396 without occlusion. Furthermore, a consistent difference in efficacy will be necessary to justify the relatively lower tolerance and higher cost of an occlusive dressing, and this study will help determine which form of dressing should be used.

Extensive objective and subjective local tolerance data will also be captured during this trial, as well as surrogate markers (parasite loads and aminoglycosides concentration in the deep dermis) that may help to determine the optimal number and duration of treatments. Finally, this study, which will be conducted from October 2005 through March 2007, will bridge the time gap between the 2004 Phase 2 study and the planned 2006 Phase 3 study. This will serve to keep the clinical team in Tunisia active and ready to start the next trial should that study be necessary.

There will be few changes to the ongoing IRB approved protocol. The study team in Tunisia and treatment schedule (daily application for 20 days) will be essentially the same, and the same facilities will be used.

3.0 STUDY SUMMARY

Fortyeight patients (48) with Old World cutaneous leishmaniasis will be randomly allocated to WR 279,396 treatment once a day for 20 days with an optimized polyurethane dressing (occlusion) (24 patients), or without occlusion (24 patients). All

patients will be rescued with the standard of care accepted in Tunisia, if the patient is not cured. The active ingredients of WR 279,396 are two aminoglycosides – paromomycin sulphate (15%) and gentamicin sulphate (0.5%) – in a base (AQIC).

Efficacy will be evaluated in terms of the number of lesions cured at D50 (D1 is the first day of treatment) with no relapse during 3 months post-treatment follow-up. Cure is defined as 100% reepitheliazation without relapse by 3 months.

Tolerance will be evaluated by local adverse reactions and by laboratory signs of systemic events.

In addition to the clinical evaluation of the CL lesions, the following parameters/clinical healing surrogates will be investigated:

- (a) parasite load will be determined in superficial and deep lesional dermis samples at D0 and D10. The mean parasite reduction ratio (parasite load at D10/parasite load at D0) in each group will be compared;
- (b) aminoglycoside concentrations (paromomycin and gentmicin) in superficial and deep infiltrated dermis in each group will be compared

One 4mm punch biopsy of the lesion randomized as explained above will be performed under epicutaneous plus transcutaneous anesthesia at day 0 and one 4 mm punch biopsy at day 10. The biopsy specimen will be divided in two: superficial dermis and deep dermis.

The results from this study will help determine the most practical treatment schedule and will answer questions that are crucial to improve the present treatment regimen with WR 279,396 which is twice a day for 20 days. This will facilitate the management of patients in the field and will help answer FDA questions during the licensing phase of the product.

4.0 STUDY OBJECTIVES

This study is designed to answer two primary questions: (a) is occlusion necessary and useful, and (b) would administration of WR 279,396 once-a-day for 20 days be as effective as twice a day for 20 days when compared to the results from study A-9768.1. The answers to these questions will help define the design of a pivotal Phase 3 study to support regulatory approval of this drug.

This study will evaluate the efficacy and tolerance of 20 days topical WR 279,396 once a day with occlusion in the treatment of Old World Cutaneous leishmaniasis. The reference schedule, i.e., 20 days topical WR 279,396 without occlusion, will be the randomized positive control group. No negative (placebo) control group will be included since the placebo cure rate has just been determined.

Decreasing the number of applications of the test drug (from 2x per day in A-9768.1) to 1x per day (this study) will likely decrease the number of times that dressing must be applied: This is expected to reduce the occurrence of AEs attributable to removal of the Tegaderm occlusive bandage. In addition, any new treatment regimen in cutaneous leishmaniasis should be amenable to local health system constraints, so our intent is to develop the simplest and shortest treatment schedule that will support easily application to all patients, especially for those in rural remote areas.

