6.2 Present topical agents

An alternative approach to a dermatological problem such as CL is a topical agent that can be applied directly to the lesion.

An Israeli topical formulation of paromomycin sulfate (15%) and methylbenzethonium chloride (12%) in soft white paraffin has been tried and is now marketed for Old World cutaneous leishmaniasis. Israeli L. major lesions treated with the formulation for 10 days cleared significantly more rapidly (100% cure at 21-30 days) than did untreated lesions on the same patients (100% cure at 51-60 days) (13). The primary agent in the topical formulation, paromomycin, is an aminoglycoside antibiotic analogous in structure to the antibacterial agent neomycin. Although neomycin is solely an antibacterial agent, paromomycin is clinically effective against protozoan and has good in vitro activity vs Leishmania amastigotes with an ED (100) of about 10 μ g ml (14). The other agent in the topical formulation, methylbenzethonium chloride (MBCL), is a cationic quaternary ammonium antibacterial disinfectant present up to 0.02% concentration in shampoos that also have good in vitro antileishmanial activity [ED (100) = 5 μ g ml] (15).

A different topical formulation of paromomycin sulfate (15%), 10 % urea in white soft paraffin was investigated in two randomized, double-blind, placebo controlled trials in children patients with L. major cutaneous leishmaniasis in Tunisia and Iran (3,4). The results were equivalent in both trials; the paromomycin ointment was safe, well tolerated and there was clear evidence of parasitologic efficacy. However, there were no clear clinical benefits with this formulation. The authors concluded that the ointment should be studied in longer or more frequent regimens in an effort to prevent parasitologic relapse and thus promote clinical improvement. In addition, these trials confirmed, that only

placebo-controlled clinical trials could demonstrate the efficacy of a new therapeutic agent in L. major CL since it is a fast healing condition.

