6.4 Clinical Efficacy of WR 279,396

6.4.1 Summary of Phase 2 studies

In 1999, a pilot phase 2 study was conducted in Colombia. This clinical study was a randomized, double blind trial of WR 279,396 compared to placebo (the cream base of WR 279,396), each administered twice-a-day for 20 days without occlusion.

In the active group in Colombia (in which WR 279,396 was applied without an occlusive dressing), 33 of 51 evaluable lesions cured (66%) at D50 and 5 lesions were non-evaluable (59% in intent-to-treat analysis). In the placebo group, 4 of 12 evaluable lesions cured (33%) at D50, and 5 lesions were non-evaluable.

There was no statistical difference between the pre-treatment sizes for cured vs failed lesions in WR 279396 patients (p = 0.7) nor in placebo patients (p = 0.8).

The 36 lesions that were treated with WR 279,396 were recognized as cured at the end of therapy on day 20 (20 lesions), at the first follow up on day 45 (13 lesions), and on day 90 (3 lesions). The 6 placebo lesions that cured were recognized on day 20 (1 lesion), day 45 (3 lesions), and day 90 (2 lesions). The mean cure time of 35 days for cured WR 279396 lesions was statistically different (p = 0.04) from the mean cure time of cured placebo lesions (56 days).

In 2003-2004, a Phase 2 study was conduced in Paris & Tunisia, Old World cutaneous leishmaniasis. 92 subjects were randomly assigned to treatment of which 90 subjects (80

from Tunisia and 10 from Paris) achieved all the follow-up period. Patients allocated treatment (n= 49) and placebo (n= 41) were similar for prognostic factors at inclusion (socio-demographic variables and clinical features of lesion). Each lesion was treated twice daily. Lesions were measured at the end of therapy, and at 50, 80 and 180 days after the institution of treatment. Cure rate at day 50 was 91.8% in the treatment group and 73.2% in controls ($x^2 = 5.60$, p= 0.017) and complete cure response was 95.8% among the former versus 75% among the latter ($x^2 = 8.04$, p= 0.004).

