6.5.4.2 Summary of a phase 2 study in the Old World

In 2003-2004, a phase 2 study was conduced in Paris & Tunisia to evaluate the efficacy of WR 279,396 as a treatment for, Old World cutaneous leishmaniasis. 92 subjects were randomly assigned to treatment of which 90 subjects achieved all the follow-up through the end of the study period. Patients were allocated treatment (n= 49) or placebo (n= 41) for 20 days twice-a-day with occlusion and followed for 6 months. Like the Colombian Phase 2 study, this study established the safety of WR 279,396. No systemic toxicity was found and only minor (grade 1) local toxicity was determined that resolved independently in 1-3 days without stopping treatment. WR 279,396 was safe, no systemic reactions were determined and no laboratory abnormalities were found. Only 22 patients (24.4%) had local reactions of short duration (1-3 days) (11 among the treatment group (22.4%) and 11 among controls (28.6%), NS) that required no treatment.

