8.0 EXPERIMENTAL PLAN

8.1 Trial Design

Fortyeight (48) patients of Old World cutaneous leishmaniasis will be randomly allocated to WR 279,396 treatment once-a-day for 20 days with occlusion (24 patients), without occlusion (24 patients). Patients not cured will be rescued with a conventional treatment accepted in Tunisia as determined by the primary care physician. The active ingredients of WR 279,396 are two aminoglycosides – paromomycin sulphate (15%) and gentamicin sulphate (0.5%) – in a base (AQIC).

Efficacy will be evaluated in terms of the number of lesions cured i.e. percentage of subjects cured at D50 (D1 is the first day of treatment) with no relapse during 3 months post-treatment follow-up. Cure is defined as 100% reepitheliazation without relapse by 3 months. Clinical improvement is defined as \geq 50% but \leq 100% reepitheliazation compared to pre-treatment lesion size at day 50 (\pm 7 days). Lack of clinical improvement at day 50 (\pm 7 days), relapse that is enlargement of the lesion compared to the previous measurement at any time after day 50 (\pm 7 days), or not demonstrating complete clinical response by 3 months will be a clinical failure. Time to cure will also be determined. Toxicity will be evaluated by local adverse reactions, and by laboratory signs of systemic events.

Induration of the lesion, as measured by the ball-pen technique, will be measured at the same time as lesion size. A photograph will be taken concurrently with these measurements to document the procedure and provide a visual record of the induration measurement and lesion size.

In addition to the clinical evaluation of the CL lesions, the following parameters/clinical healing surrogates will be investigated: (a) parasites loads will be determined in superficial and deep lesion dermis at D0 and D10. The mean parasite log-reduction ratio (log parasite load at D10/log parasite load at D0) in each group will be compared; (b) aminoglycoside concentrations in superficial and deep infiltrated dermis in each group will be compared.

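### Once daily versus twice daily is named a primary question the study is designed to answer, but both arms are once daily, so dosing frequency is confounded with study

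*Protocol*

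**What the plan says.** Section 4.0 states: "This study is designed to answer two primary questions". The first is whether occlusion is needed and useful. The second is whether treatment would, "once-a-day for 20 days be as effective as twice a day for 20 days when compared to the results from study A-9768.1". The same section says the answers will help define the design of a pivotal Phase 3 study. Section 7.0 repeats both as major questions for choosing the Phase 3 arms. Sections 3.0 and 8.1 say the results will answer questions crucial to improving the current twice-daily regimen.

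The design in Section 8.1 is "once-a-day for 20 days with occlusion (24 patients), without occlusion (24 patients". Section 4.0 adds: "No negative (placebo) control group will be included since the placebo cure rate has just been determined". The sample size in Section 9.1 concerns only the gain from occlusion, and the Fisher test in Section 9.2 compares only the two WR 279,396 groups of this trial.

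The comparator, A-9768.1, ran in 2003-2004 in Paris and Tunisia and gave drug or placebo "for 20 days twice-a-day with occlusion and followed for 6 months" (Section 6.5.4.2). Day-50 cure was 91.8% on drug (n=49) and 73.2% on placebo (n=41) (Section 6.4.1).

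**The concern.** A question that a study is said to be designed to answer needs a contrast within that study. Here no patient receives the twice-daily regimen. Any difference or similarity between the once-daily arms and A-9768.1 combines the effect of frequency with everything else that changed: the calendar period, a dressing that Section 3.0 calls optimized, and the loss of the Paris patients. The non-occluded arm also differs from A-9768.1 on occlusion itself, so at most half the trial bears on the question.

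What is at stake is the Phase 3 regimen. If the occluded arm shows a rate near 90%, the wording of Section 4.0 invites the conclusion that once daily is as effective. The data would also be compatible with a substantial loss.

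**Working it through.** **Inputs.** A-9768.1, Section 6.4.1: 91.8% of 49 = 45 cured; 73.2% of 41 = 30 cured; difference 91.8 - 73.2 = 18.6 points. This trial: 24 in the occluded arm (Sections 3.0 and 8.1), or 20 under Section 9.1. The protocol states no margin for question (b), so 5, 10 and 15 points are taken as assumptions.

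**1. The plan's own figure.** Section 9.1 assumes 60% against 95% at one-sided 5% and 80% power, with 20 per arm. The exact power of a one-sided Fisher test with 20 per arm is 80.8%, so the figure reproduces. It sizes the occlusion contrast and nothing else.

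**2. Precision of the cross-trial difference.** Suppose the occluded once-daily arm cures 22/24 = 91.7%, essentially the A-9768.1 rate. The 95% Wilson limits are 0.742 to 0.977 for 22/24 and 0.808 to 0.968 for 45/49. With Newcombe's method:

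- difference = 0.9167 - 0.9184 = -0.002
- lower limit = -0.002 - √[(0.9167 - 0.7415)² + (0.9678 - 0.9184)²] = -0.184
- upper limit = -0.002 + √[(0.9768 - 0.9167)² + (0.9184 - 0.8081)²] = +0.124

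The lower limit of -18.4 points is almost the whole 18.6-point drug-placebo difference. With 20 in the arm, 18/20 gives -22.5 to +11.3 points.

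**3. Chance of excluding a loss when there is none.** Both true rates are set to 91.8%. All outcomes for 24 and 49 patients are enumerated, and the binomial probabilities are summed wherever the Newcombe lower limit lies above minus the margin.

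| Assumed margin | One-sided 5% | One-sided 2.5% |
|---|---|---|
| 5 points | 13.0% | 5.3% |
| 10 points | 31.6% | 16.3% |
| 15 points | 58.2% | 40.5% |

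**4. Chance of missing a complete loss.** If once daily truly cured only 73.2%, the A-9768.1 placebo rate, a two-sided 5% Fisher test of 24 against 49 would be significant about 46% of the time. About 54% of such trials would show no significant difference.

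**5. Scale of a randomised answer.** For a concurrent comparison with both rates at 91.8%, one-sided 2.5% and 80% power, n per arm = (1.960 + 0.842)² × 2 × 0.918 × 0.082 / margin². This gives 473, 119 or 53 per arm for margins of 5, 10 or 15 points.

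Steps 2 to 4 treat the two trials as if randomised against each other. They contain no allowance for between-trial bias and so favour the protocol.

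**The case against.** Section 7.0 calls this a pilot proof-of-concept study, the historical comparator is disclosed in the objective itself, the answers only help define Phase 3, and no formal equivalence claim is made. All of that is true. It lowers the weight of the point, but it does not make the second question one that this design can answer.

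A reader might infer more than the documents support:

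- **That control rates drift by 48 points between trials (25% against 73.2%).** Section 2.0 says: "The global healing rate is already much higher than the previous (placebo) 25% healing rate in the same area using the same evaluation criteria". It then suggests that the occlusive dressing contributed, and Section 6.2 shows that the Tunisian trial used a different vehicle. Rates without active drug did differ widely, but the gap is not a measure of pure drift, nor of the bias between two occluded WR 279,396 arms.
- **That the protocol rules out its own comparison.** Section 6.2 reports that only "placebo-controlled clinical trials could demonstrate the efficacy of a new therapeutic agent in L. major CL since it is a fast healing condition". This concerns showing that a new agent works, not comparing schedules of a drug already tested against placebo.
- **That unequal follow-up invalidates the comparison.** For A-9768.1, Section 6.4.1 states: "Lesions were measured at the end of therapy, and at 50, 80 and 180 days after the institution of treatment". Follow-up here ends at about day 90, but both trials assess cure at day 50.
- **That site mix is a major confounder.** Of 90 completers in A-9768.1, 80 were Tunisian, and Section 2.0 keeps essentially the same Tunisian team and the same facilities. Site mix is a minor factor.
- **That the lack of a margin or analysis in Section 9 is itself a fault.** Those could sit in a statistical analysis plan that is not shown.

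Precision is also not hopeless for every outcome. A result of 24/24 has a lower limit of -6.5 points, which would exclude a 10-point loss but not a 5-point one.

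**Conclusion.** The point holds in a limited form. The protocol calls the frequency question primary and says that the study is designed to answer it, but the design contains no contrast in frequency. No analysis plan could create one, so a conclusion of equal efficacy cannot be supported.

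Sampling error alone leaves an interval of about -18 to +12 points when the observed rates match. The chance of excluding a true-zero loss runs from 13% to 58% at one-sided 5%, and from 5% to about 40% at one-sided 2.5%. These figures assume 24 occluded patients, true rates of 91.8% in both trials, margins of 5 to 15 points chosen for illustration, and no between-trial bias.

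Nothing here shows that once daily is less effective. The randomised comparison of occlusion and its stated sample size are not affected.

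**What to change.** In Sections 4.0 and 7.0, keep question (a), occlusion, as the only primary question, and drop the statement that the study is designed to answer (b). Recast (b) along these lines:

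*Descriptive: day-50 cure in the occluded once-daily arm, with exact 95% confidence interval, shown beside day-50 cure in the occluded twice-daily arm of A-9768.1. No conclusion of equal efficacy will be drawn.*

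In Sections 3.0 and 8.1, bring the statements that the results will answer questions about the twice-daily regimen into line with this.

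The cost is wording only: no patients, visits or procedures change. The sponsor gives up a claim that the design cannot support.

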5.0 FACILITIES TO BE USED

Patients with presumed leishmaniasis would be screened in the endemic area of Sidi Bouzid and El Mnara and examined and enrolled in the study by a team from the Institut Pasteur in Tunisia. Patients will be treated as outpatients. This area has a laboratory that routinely performs standard clinical tests (urinalysis, serum chemistries, complete blood counts). All the parasitological exams will be done at the Clinical Laboratory of the regional hospital of Sidi-Bouzid in Tunisia.

6.0 BACKGROUND OF LEISHMANIASIS

6.1 Natural history and drug treatment of Old World cutaneous leishmaniasis

6.1.1 Old World cutaneous leishmaniasis

Cutaneous leishmaniasis typically presents as a papule that enlarges over approximately 1 month into an ulcer with raised edges and a necrotic center (1). The mean area per ulcer in one study was 400 mm2 (2). Nevertheless, rare ulcers are 2,000 mm², and a rare patient may have 20 ulcers. The spontaneous cure rate over 6-8 weeks for cutaneous leishmaniasis caused by members of the L. major or L. tropica complex in the Old World ranges from 15-45% (3,4). The most reliable figures come from L. major disease in Tunisia and Iran, for which rates of 20-44% are reported (3,4). Although frequently follow-up in such studies is performed for 1 year, in a recent study of 27 relapsed lesions (5), only 2 occurred between 6 and 12 months after the end of therapy, and follow up for 6 months therefore seems sufficient.

Standard treatment is with intralesional injections of pentavalent antimonials. When 1-3 ml of Glucantime were administered intradermally once a week for 5 consecutive weeks to 20 patients with L. tropica in Syria, a cure rate of 76% was achieved (6). This regimen of Glucantime is considered successful in most L. tropica or L. major endemic areas, although these results are substantiated by only one controlled study. However, the regimen requires at least five painful intradermal injections which can hardly be performed in children and/or when lesions are located near eyes, mouth or nose. The overall cost of one intradermal injection is about \$30 in France; \$150 for a complete treatment course. For multiple and/or periorificial lesions that can't be injected, standard treatment is with pentavalent antimonials intramuscular at a dosage of 10-20 mg antimony (Sb)/kg/day for

10-20 days. This regimen of Pentostam or Glucantime is successful in Central and South America with a ~90% cure rate with 1 year follow up. A lower cure rate (50%) of cutaneous leishmaniasis was achieved in Algeria in a L. major endemic area (7). The regimen requires 20 days of injections for an outpatient dermatological disease, is expensive (~US\$200 per course), and is potentially or frankly toxic to the heart, liver, pancreas, hematopoietic system, and musculoskeletal system (8).

The attempt to find alternatives to the above antimonial regimen has included oral agents such as ketoconazole, fluconazole and allopurinol, and short courses of antimonials and pentamidine. The oral agents have not been shown to be >75% curative (8, 35). On the other hand, a 10 day course of Pentostam, 20 mg/kg/day intravenously for 10 days (9), and a 4-injection course of pentamidine administered over 7 days (3 mg/kg qod for 4 injections)(9) have been reported to be ~90% curative in the New World.

